### 6.2.3 Trametinib and GSK2141795 Dose Modification for Rash

Two types of rashes may be seen with the trametinib and GSK2141795 combination:

1. Acneiform rash, typically associated with MEK inhibitor therapy (trametinib).
2. Maculopapular rash, often associated with pruritus (GSK2141795).

If the diagnosis is unclear, a biopsy and photographs should be obtained as well as a dermatology consult. In addition, if the investigator feels the rash is not consistent with a MEK inhibitor-associated acneiform rash and is  $\geq$  Grade 2, a skin punch biopsy should be performed.

In general, topical and oral antibiotics (doxycycline or minocycline) play a larger role in management of the MEK inhibitor acneiform rash, while topical and oral steroids are more relevant to the management of the AKT inhibitor maculopapular rash.

The institutional standards for the management of skin-related AEs can differ from these

guidelines. In this case, best clinical judgment should be applied and a consultation with the study chair or the CTEP Medical Monitor may be required.

Dose Modification Guidelines and Management for Rash		
Rash Severity	Management Guideline	Dose Modification
Grade 1	
 
• Initiate prophylactic and symptomatic treatment measures.
 
• Use moderate strength topical steroid.
 
• Reassess after 2 weeks.
 
	
 
• Continue treatment.
 
• If rash does not recover to baseline within 2 weeks despite best supportive care, reduce trametinib or both agents by one dose level.
 

Grade 2	
 
• Initiate prophylactic and symptomatic treatment measures.
 
• Use moderate strength topical steroid.
 
• Reassess after 2 weeks.
 
	
 
• Continue treatment
 
• Reduce trametinib or both agents by one dose level.
 
• If rash recovers to ≤ grade 1 within 2 weeks, increase dose(s) to previous dose level.
 
• If no recovery to ≤ grade 1 within 2 weeks, interrupt treatment until recovery to ≤ grade 1.
 
• Restart trametinib or both agents at reduced dose level.
 

Grade ≥3	
 
• Use moderate strength topical steroids PLUS oral methyl-prednisolone dose pack.
 
• Consult dermatologist.
 
	
 
• Interrupt trametinib or both agents until rash recovers to ≤ grade 1.
 
• Restart with trametinib or both agents with one dose level reduction.
 
• If no recovery to ≤ grade 2 within 3 weeks, permanently discontinue both agents (resumption of trametinib or GSK2141795 alone may be considered based on toxicity-benefit consideration and after consultation with CTEP).
 

1. Rash prophylaxis is recommended for the first 6 weeks of study treatment (refer to guidelines for trametinib).
 
2. Moderate-strength topical steroids: Hydrocortisone 2.5% cream or fluticasone propionate 0.5% cream.
 
3. Trametinib or GSK2141795 may be escalated to previous dose level if no rash is evident 4 weeks after restarting study treatment.
		

#### 6.2.4 Trametinib and GSK2141795 Dose Modifications for Liver Chemistry Changes

Dose Modification for Liver Function Test Abnormalities

Liver chemistry stopping criteria are defined as follows. When any of the liver chemistry stopping criteria are met, immediately discontinue trametinib and GSK2141795, perform liver event follow-up assessments, and monitor the patient until liver chemistries resolve, stabilize, or return to baseline values.
 
 
• ALT <math>\geq 3</math>x ULN and bilirubin <math>\geq 2</math>x ULN (<math>>35\%</math> direct bilirubin) (or ALT <math>\geq 3</math>x ULN and international normalized ratio [INR] <math>>1.5</math>x ULN, if INR measured). NOTE: If serum bilirubin fractionation is not immediately available, treatment should be discontinued if ALT <math>\geq 3</math>x ULN and bilirubin <math>\geq 2</math>x ULN. Serum bilirubin fractionation should be performed if testing is available. If testing is unavailable, record presence of detectable urinary bilirubin on dipstick, indicating direct bilirubin elevations and suggesting liver injury.
 
• ALT <math>\geq 5</math>x ULN.
 
• ALT <math>\geq 3</math>x ULN if associated with the appearance or worsening of symptoms of hepatitis or hypersensitivity such as fatigue, nausea, vomiting, right upper quadrant pain or tenderness, fever, rash, or eosinophilia.
 
• ALT <math>\geq 3</math>x ULN persisting for <math>\geq 4</math> weeks.
 
• ALT <math>\geq 3</math>x ULN and cannot be monitored weekly for 4 weeks.
 

#### 6.2.5 Trametinib and GSK2141795 Dose Modification for Hypertension, Pneumonitis, and Visual Disturbance

- These AEs are typically associated with trametinib. Please follow guidelines for trametinib.
- GSK2141795 may continue when trametinib is on hold if AEs are  $\leq$  grade 2.
- If the above AEs are grade 3-4, GSK2141795 should be held when trametinib is held. Once the AEs have resolved to grade 1 or baseline, GSK2141795 may resume at the same dose.
- If GSK2141795795 has been held for  $>21$  days, a discussion with the CTEP drug monitor is required before resuming treatment with the agent.

#### 6.2.6 Trametinib and GSK2141795 Dose Modifications for Reduced LVEF

Decreases of the left ventricular ejection fraction (LVEF) have been observed in patients receiving trametinib. GSK2141795 dose is to be modified the same as for trametinib. ECHOs must be performed in regular intervals outlined in the Study Calendar. The same procedure (either ECHO or MUGA, although ECHO is preferred) should be performed at baseline and at follow-up visit(s).

Dose Modification Guidelines and Stopping Criteria for LVEF Decrease		
Clinic	LVEF-drop (%) or CTC/AE grade	Action and Dose Modification
Asymptomatic	Absolute decrease of $>10\%$ in LVEF compared to baseline and ejection fraction below the institution's LLN.	
 
• Follow the instructions for trametinib. When trametinib is on hold, GSK2141795 should be on hold.
 

Dose Modification Guidelines and Stopping Criteria for LVEF Decrease		
Clinic	LVEF-drop (%) or CTCAE grade	Action and Dose Modification
Symptomatic b	
 
• Grade 3: resting LVEF 39% or >20% absolute reduction from baseline
 
• Grade 4: Resting LVEF ≤20%.
 
	
 
• Permanently discontinue trametinib and GSK2141795
 
• Report as SAE.
 
• Consult with cardiologist.
 
• Repeat ECHO after 2, 4, 8, 12, and 16 weeks or until resolution.
 

If ECHO does not show LVEF recovery after 2 weeks, repeat ECHO 2 weeks later. Symptoms may include: dyspnea, orthopnea, and other signs and symptoms of pulmonary congestion and edema.		

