## 3. PATIENT SELECTION

### 3.1. Eligibility Criteria

- 3.1.1 Patients must have histologically or cytologically confirmed metastatic invasive breast cancer that is negative for the estrogen receptor (ER), progesterone receptor (PR) and HER2 by institutional guidelines.
- 3.1.2 Patients must have measurable disease (RECIST 1.1).
- 3.1.3 Patients must have had exposure to at least 1 and no more than 3 prior chemotherapy regimens for the treatment of metastatic breast cancer.
- 3.1.4 Patients must consent to both a pretreatment and a post-treatment mandatory research biopsy prior to enrolling on trial, and therefore, must have tissue (excluding bone or brain) that is amenable to biopsy.
- 3.1.5 Age  $\geq 18$  years. Because no dosing or adverse event data are currently available on the use of trametinib monotherapy or in combination with GSK2141795 in patients  $< 18$  years of age, children are excluded from this study, but will be eligible for future pediatric trials.
- 3.1.6 ECOG performance status 0-1 ([Appendix A](#)).

- 3.1.7 Life expectancy of greater than 3 months.
- 3.1.8 Able to swallow and retain orally-administered medication and does not have any clinically significant gastrointestinal abnormalities that may alter absorption such as malabsorption syndrome or major resection of the stomach or bowels.
- 3.1.9 All prior treatment-related toxicities must be CTCAE v5 grade  $\leq 1$  (except alopecia) at the time of enrollment.
- 3.1.10 Patients must have normal organ and marrow function as defined below:
- Absolute neutrophil count  $\geq 1,500/\text{mcL}$
  - Platelets  $\geq 75,000/\text{mcL}$
  - Total bilirubin  $\leq 1.5 \times$  institutional upper limit of normal
  - AST(SGOT)/ALT(SGPT)  $\leq 2.5 \times$  institutional upper limit of normal
  - LVEF  $\geq$  institutional lower limit of normal by ECHO or MUGA
  - Serum creatinine  $\leq 1.5 \text{ mg/dL}$  OR calculated creatinine clearance (Cockcroft-Gault formula)  $\geq 50 \text{ mL/min}$  OR 24-hour urine creatinine clearance  $\geq 50 \text{ mL/min}$
- 3.1.11 Patients must have controlled blood pressure with a systolic blood pressure  $< 140 \text{ mmHg}$  and diastolic  $< 90 \text{ mmHg}$ . Anti-hypertensive medications are permitted.

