### 6.1.7 Trametinib Dose Modification for Reduced LVEF

Decreases of the left ventricular ejection fraction (LVEF) have been observed in patients receiving trametinib. Therefore, ECHOs must be performed in regular intervals outlined in the Study Calendar. The same procedure (either ECHO or MUGA, although ECHO is preferred) should be performed at baseline and at follow-up visit(s).

Trametinib Dose Modification Guidelines and Stopping Criteria for LVEF Decrease		
Clinic	LVEF-drop (%) or CTCAE grade	Action and Dose Modification
Asymptomatic	Absolute decrease of >10% in LVEF compared to baseline and ejection fraction below the institution's LLN.	
 
• Interrupt trametinib and repeat ECHO within 2 weeks.a
 
• If the LVEF recovers within 4 weeks (defined as LVEF <math>\geq</math>LLN and absolute decrease <math>\leq</math>10% compared to baseline):               
 
– Consult with the CTEP trametinib medical monitor and request approval for restart.
 
– Restart treatment with trametinib at reduced dose by one dose level.
 
– Repeat ECHO 2, 4, and 12 weeks after re-start; continue in intervals of 12 weeks thereafter.
 
 
 
• If LVEF does not recover within 4 weeks:               
 
– Consult with cardiologist.
 
– Permanently discontinue trametinib.
 
– Repeat ECHO after 2, 4, 8, 12, and 16 weeks or until resolution.
 
 
 

Symptomaticb	
 
• Grade 3: resting LVEF 39-20% or >20% absolute reduction from baseline
 
• Grade 4: Resting LVEF <math>\leq</math>20%.
 
	
 
• Permanently discontinue trametinib.
 
• Report as SAE.
 
• Consult with cardiologist.
 
• Repeat ECHO after 2, 4, 8, 12, and 16 weeks or until resolution.
 

a If ECHO does not show LVEF recovery after 2 weeks, repeat ECHO 2 weeks later.
 
b Symptoms may include: dyspnea, orthopnea, and other signs and symptoms of pulmonary congestion and edema.
		

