## 6.2. Dose Modifications for Part 2 Trametinib Combined with GSK 2141795

If a participant had a dose reduction of trametinib during Part 1, the participant will continue on this dose at the commence of Part 2 of the study. If no dose reductions occurred, the patient will start on trametinib at the recommended dose of 1.5 mg oral daily for Part 2. GSK2141795 will be added at time of entry into Part 2 to trametinib, beginning at dose level 0.

Dose Level	Trametinib Dose/Schedule
0	1.5 mg daily
-1	1 mg daily

Dose Level	GSK2141795 Dose/Schedule
0	50 mg daily
-1	25 mg daily

**NOTE:** AEs occurring in patients treated with GSK2141795 and trametinib may be related to 1) overlapping toxicities between the two agents (*e.g.*, rash and diarrhea); 2) toxicities typically associated with trametinib (*e.g.*, visual disturbance) or GSK2141795 (*e.g.*, hyperglycemia or hypoglycemia). However, toxicities associated with individual agents may be potentiated in the combination, or unanticipated AEs may occur.

The dose modifications may involve one or both agents, and should be based on the nature, severity and attributions of the AEs. General guidelines are provided below. CTEP drug

monitors should be consulted if there are questions about the attribution of AEs and how the doses should be modified.

6.2.1 Trametinib and GSK2141795 Dose Modification for Toxicities Not Specified in Subsequent Sections

Toxicity Grade a	Dose Modification
Grade 1	Continue at current dose level. Consider supportive care recommendations.
Grade 2	Consider withholding dose of trametinib and/or GSK2141795 until toxicity resolves to grade 1 or baseline. Upon resolution, then restart at current dose level. Consider supportive care recommendations.
Grade 3	Withhold dose until toxicity resolves to grade 1 or baseline. Upon resolution, resume at the next lower dose level of both trametinib and/or GSK2141795. Consider supportive care recommendations.
Grade 4	Permanently discontinue trametinib and GSK2141795.

a: the guidelines are for AEs thought to be related to GSK2141795 and/or trametinib. However, temporary interruption of the agent should be considered if the patient is critically ill due to AEs of any attribution

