### Study Calendar

Study Assessment s 	Screen	Part 1 Trametinib monotherapy	Part 2 Trametinib in combination with GSK2141795	Final Study Visit 	Post Treatment Follow Up 
Informed Consent	X				
Baseline Demographics	X				
Medical History / Interim History	X	Day 1 ( $\pm 3$ days) of each cycle	Day 1 ( $\pm 3$ days) of each cycle	X	
Concomitant Medications	X	Continuous			
Physical Exam	X	Day 1 ( $\pm 3$ days) of each cycle	Day 1 ( $\pm 3$ days) of each cycle	X	
ECOG Performance Status	X	Day 1 ( $\pm 3$ days) of each cycle	Day 1 ( $\pm 3$ days) of each cycle	X	
Vital Signs (BP, HR, Temperature, weight)	X	Day 1 ( $\pm 3$ days) of each cycle	Day 1 ( $\pm 3$ days) of each cycle	X	
Hematology, Clinical Chemistry 	X	Day 1 ( $\pm 3$ days) of each cycle	Day 1 ( $\pm 3$ days) of each cycle	X	
Pregnancy Test 	X				
Hemoglobin A1C, TSH, fasting glucose	X	Repeated every 3 cycles $\pm 7$ days or as Clinically Indicated			
Fingerstick blood glucose			At home daily monitoring for weeks 1 -4, then as clinically indicated	As Clinically Indicated	
12-Lead ECG	X		Prior to dosing on Week 1 day 1 and day 15, and then every 4 weeks (Week 5, Week 9, etc.) $\pm 7$ days or as clinically indicated		

Study Assessments 	Screen	Part 1 Trametinib monotherapy	Part 2 Trametinib in combination with GSK2141795	Final Study Visit 	Post Treatment Follow Up 
LVEF (ECHO)	X	Repeated every 3 cycles $\pm$ 7 days during Part 1 or as Clinically Indicated	Week 5, Day 1 of Part 2 and then at the start of every 12 weeks $\pm$ 7 days or as clinically indicated	As Clinically Indicated	
Ophthalmic Exam 	X	As Clinically Indicated			
Blood sample 		Day 1 ( $\pm$ 3 days) of cycle 1			
Plasma 	X	Day 1 cycle 2 and at progression	Day 1 of cycle 2 (prior to dosing)	X	
Research Biopsy(s) 	Mandatory research biopsies will be attempted on all patients prior to the initiation of study treatment on Part 1	Mandatory research biopsies will be attempted on all patients at time of progression on Part 1	Optional research biopsies will be attempted on patients at time of progression on Part 2		
Study Agents		Trametinib will be administered daily in Part 1. Trametinib will be administered in combination with GSK2141795 in Part 2. Please see Section 6 for Dose Modifications.			

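### The Part 2 stopping rule for symptomatic LVEF decline prints a single value, 39%, where the matching Part 1 rule prints the range 39-20%

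*Combined protocol and SAP*

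**What the plan says.** Section 6.1.7 (Part 1, trametinib alone) lists three triggers for a symptomatic patient. The Grade 3 line reads "Grade 3: resting LVEF 39-20% or" an absolute fall of more than 20 points from baseline, and Grade 4 is a resting value of 20% or less. Any of them means permanent discontinuation, an SAE report, a cardiology consult and a set schedule of repeat echocardiograms.

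Section 6.2.6 (Part 2, the combination) has the same row. Its Grade 3 line reads "Grade 3: resting LVEF 39% or" more than "20% absolute reduction from baseline". Grade 4 is again 20% or less. The action is "Permanently discontinue trametinib and GSK2141795", with the same SAE report, consult and repeat schedule.

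Three other provisions bear on the size of the problem:

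- **Baseline.** Section 3.1.10 requires LVEF at or above the "institutional lower limit of normal by ECHO or MUGA" and gives no percentage. The Study Calendar lists no LVEF measurement at entry to Part 2; the first is at "Week 5, Day 1 of Part 2 and then at the start of every 12 weeks".
- **Cross-references.** The opening text of Section 6.2.6 ties changes in GSK2141795 dose to those for trametinib. The instruction to follow the trametinib rules stands only in the asymptomatic row. Sections 6.2.7 and 6.2.8, by contrast, name Sections 6.1.8 and 6.1.9 outright.
- **Consultation.** Under Section 6.2, the CTEP drug "monitors should be consulted if there are questions about the attribution of AEs and how the doses should be modified".

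**The concern.** A single value with no inequality sign cannot work as a threshold for a continuous measure. Everything else in the two rows matches, and nothing in the protocol suggests that the combination was meant to have a narrower stopping rule than monotherapy. No other section gives a numeric Part 2 trigger that would settle the matter.

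The row decides whether a patient with cardiac symptoms stops both drugs for good, and it also prompts the SAE report and the cardiology consult. Section 7.1.1.1 lists heart failure, left ventricular systolic dysfunction and decreased ejection fraction as possible effects of trametinib. Section 7.1.1.2 lists the last two for GSK2141795 with the relationship undetermined. The rule for the combination should be at least as clear as the rule for one drug.

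**Working it through.** The plan has no calculated figure to reproduce here. The check compares the two rules as printed.

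**Inputs.** Let B be baseline LVEF and L the current resting LVEF, both in percent, in a symptomatic patient. B is taken as the screening value because the Study Calendar has no measurement at Part 2 entry. The values of B below are assumptions.

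**Rules.**

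- Part 1 (6.1.7): stop if 20 ≤ L ≤ 39, or B − L > 20, or L ≤ 20.
- Part 2 as printed (6.2.6): stop if L = 39, or B − L > 20, or L ≤ 20.

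**Gap.** A patient stops under Part 1 but meets no printed Part 2 trigger when 20 < L < 39 and B − L ≤ 20. In whole percentages, L then runs from max(21, B − 20) to 38, and the number of values is 38 − max(21, B − 20) + 1.

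| Assumed baseline | Lower end, B − 20 | Uncovered LVEF | Whole-percent values |
|---|---|---|---|
| 45% | 25 | 25-38% | 14 |
| 50% | 30 | 30-38% | 9 |
| 53% | 33 | 33-38% | 6 |
| 55% | 35 | 35-38% | 4 |
| 58% | 38 | 38% only | 1 |
| 59% or above | 39 or more | none | 0 |

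The gap closes at 59% because a fall of more than 20 points from there covers everything below 39%. The same cut-off holds in steps of 0.1%: at a baseline of 58.9% only 38.9% is uncovered, and at 59.0% nothing is.

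**Example.** Take B = 53 and L = 35. The fall is 53 − 35 = 18, which is not more than 20, and 35 is neither 39 nor at most 20. No printed Part 2 trigger is met. Under Part 1, 35 lies within 39-20 and trametinib stops permanently.

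**After correction.** With 39-20% in the Part 2 cell the two rules are identical and the gap is empty at every baseline.

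**The case against.** The strongest reply is that the protocol itself may be correct. The Part 2 table is split across pages, its header appears twice with different spellings, and its footnotes have lost the labels that the Part 1 footnotes keep. A dropped -20 would be a fault of the same kind. This cannot be ruled out without the source page. Against it, the rest of the cell is intact and the Part 1 cell came through whole, so the lost labels do not show that the range was lost too.

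The second reply is that nobody would read the cell literally. It is labelled Grade 3 and sits directly above a Grade 4 that starts at 20%, so Grade 3 must run down to that point. The sentence tying GSK2141795 to trametinib points the same way. This largely stands and is why the risk is low. But that sentence does not restate the number, and the symptomatic row has no cross-reference.

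The third reply is that other text would catch the patient. The asymptomatic row does not apply to a patient with symptoms, and even there restart follows only recovery of LVEF and the instruction "Consult with the CTEP trametinib medical monitor and request approval for restart". Section 5.4 lets the investigator end treatment for unacceptable adverse events. The general table in Section 6.2.1 would withhold treatment at Grade 3, but it is meant for toxicities without their own section and allows resumption at a lower dose, which is weaker than permanent discontinuation. These provisions reduce the risk; none of them supplies the missing threshold.

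Finally, the width of the gap rests on assumed baselines. That is correct, and the number of patients affected cannot be stated.

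**Conclusion.** The inconsistency is real in the text as read, and minor. The Part 2 cell is wrong as printed: taken literally it omits LVEF from max(21, baseline − 20) to 38%. The omission narrows as baseline rises and vanishes at 59%. The intended range is almost certainly 39-20%, and a copying slip is the likeliest cause. The conclusion assumes that the source page matches the text available here and that baseline means the screening measurement. Confidence is medium because of the first assumption. Sample size, endpoints and analysis are untouched.

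**What to change.** Check the source page of Section 6.2.6. If it shows the single value, either change the Grade 3 line so that it begins "Grade 3: resting LVEF 39-20% or", leaving the rest of the line as it is, or replace the symptomatic criteria with a reference to Section 6.1.7, as Sections 6.2.7 and 6.2.8 already do for their own topics.

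The cost is one table cell. Section 13.2 reports the consent of 50 patients in the past tense, so the correction helps only those still on Part 2 or yet to start it. A clarification memo or the next routine amendment is enough.

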#### 6.2.7 Trametinib and GSK2141795 Dose Modification for QTc Prolongation

GSK2141795 is not well known to cause prolongation of the QTc. Therefore, for QTc prolongation, participants should undergo dose modifications of trametinib as listed for Part 1 in **Section 6.1.8** and GSK2141795 should be continued at the same dose. GSK2141795 may be continued as monotherapy if trametinib must be permanently discontinued if otherwise tolerated.

#### 6.2.8 Trametinib and GSK2141795 Dose Modification for Hypertension

GSK2141795 is not well known to cause hypertension. Therefore, for hypertension, participants should undergo dose modifications of trametinib as listed for Part 1 in **Section 6.1.9** and GSK2141795 should be continued at the same dose or held and resumed as detailed in **Section 6.2.5** depending on the grade of the hypertension. GSK2141795 may be continued as monotherapy if trametinib must be permanently discontinued if otherwise tolerated.

#### 6.2.9 Trametinib and GSK2141795 Dose Modifications for Hypo- or Hyperglycemia

GSK2141795 may cause hypo- or hyperglycemia. Trametinib is not known to cause hypo- or hyperglycemia. Subjects will be required to monitor their blood glucose each morning preprandial during Part 2 of the study while receiving GSK2141795 and record the results in the provided diary ([Appendix F](#)). Subjects should contact their study doctor for readings ≤ 70 or ≥ 250 for physician instructions and management.

Management and Dose Modification Guidelines for Hypo- or Hyperglycemia		
Criteria	Management Guidelines	Study Drug Modification
(For management purposes, refer to mild, moderate and severe intensity criteria; however for eCRF reporting use NCI-CTCAE version 5.0 Grades 1-5)		
Mild  Fasting blood glucose > 150mg/dL	Monitor fasting and preprandial glucose.	Continue study drug
Moderate to Severe  Fasting blood glucose <70 mg/dL OR any blood glucose > 250mg/dL	
 
• If a blood glucose >250 mg/dL, monitor for ketoacidosis as clinically indicated.
 
• When managing hyperglycemia associated with GSK2141795, be aware that the action of insulin or other antihyperglycemic agents (e.g., sulfonylureas, biguanides, etc.) may be substantially blocked by the study agent. However the action of antihyperglycemic agents would be restored as GSK2141795 is cleared. The patient should be observed closely for rebound hypoglycaemia as GSK2141795 is held/or discontinued.
 
• Intravenous insulin treatment is recommended.
 
	Hold drug(s) and notify investigator immediately. The investigator should discuss intervention and possible resumption of study drug(s) with the CTEP monitor.

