Rash: Rash may or may not be associated with pruritis. Preliminary data suggest that drug interruption and dose reduction upon re-challenge ameliorate the symptoms. Rash management should focus on symptom relief and maintenance of an intact integument. Dermatology consult is recommended when clinically appropriate. Topical steroid creams have been found to provide some relief from symptoms.

Hyperglycemia: Hyperglycemia occurred in patients receiving  $\geq 75$  mg/day with the majority of events occurring at doses exceeding the MTD of 75 mg/day. Treatment-related grade 3 or grade 4 events were observed at 75 mg, 100 mg, and 150 mg daily doses. The frequency and severity of hyperglycemia AEs is reduced at the 75mg/day dose as compared with higher doses. It is not clear if oral anti-hyperglycemic drugs are useful to ameliorate the hyperglycemia, although both intravenous and sliding scale insulin have been helpful.

Hypoglycemia: Asymptomatic hypoglycemia occurred in patients receiving  $\geq 75$  mg/day. Treatment-related grade 3 or grade 4 events were observed at 75 mg and 100 mg daily doses. The mechanism of hypoglycemia is currently unknown.

Thyroid Events: Reversible minimal to mild hypertrophy of follicular cells was seen in the thyroid glands of dogs given 5 mg/kg/day for 4 weeks. The relationship to GSK2141795 and clinical significance are unknown, although three cases of drug-related hypothyroidism have been reported

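### Section 6.2.9 glucose table: the intravenous insulin recommendation carries no high-glucose condition, so as written it also applies to fasting glucose below 70 mg/dL

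*Combined protocol and SAP*

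**What the plan says.** Section 6.2.9 governs glucose disturbances in Part 2, when GSK2141795 is added to trametinib. Patients test their glucose at home: "Subjects should contact their study doctor for readings" of 70 or lower, or 250 or higher.

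The table that follows has two rows. The Mild row covers only raised fasting glucose (above 150 mg/dL). The Moderate to Severe row covers both directions: "Fasting blood glucose <70 mg/dL OR any blood glucose > 250mg/dL". It has one management cell with three bullets:

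1. monitoring for ketoacidosis, restricted to glucose above 250 mg/dL;
2. a caution on drug effect, which opens "When managing hyperglycemia associated with GSK2141795, be aware that the action of insulin" and goes on to warn that this action may be blocked while GSK2141795 is present;
3. "Intravenous insulin treatment is recommended".

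The study drug column, also shared by both triggers, says "Hold drug(s) and notify investigator immediately", after which the investigator is to discuss intervention with the CTEP monitor.

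**The concern.** The third bullet stands in a cell that applies equally to low and high glucose, and nothing in it limits it to high glucose. Someone who enters the row because fasting glucose is below 70 mg/dL finds that the first two bullets exclude themselves by their own terms. The only treatment recommendation left is insulin, which would lower glucose further.

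What is at stake is patient safety, not inference. A dose-modification table is operative text, and it should be correct when followed as written, without relying on the reader to notice that one line must be ignored.

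**Working it through.** No arithmetic decides this point and the plan states no figure to reproduce. The check is a comparison of texts.

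**Step 1: the condition on each part of the row (Section 6.2.9).**

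| Part of the row | Stated condition | Applies below 70 mg/dL as written? |
|---|---|---|
| Bullet 1, ketoacidosis | glucose above 250 mg/dL | No |
| Bullet 2, blocked insulin action and rebound | managing hyperglycemia | No |
| Bullet 3, intravenous insulin | none | Yes |
| Study drug column, hold and notify | none | Yes |

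Two of three bullets are limited and one is not. For the study drug column, having no condition is right, because the hold is meant for both triggers. For bullet 3 it is not.

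**Step 2: does the condition appear elsewhere?** The Hyperglycemia paragraph of the GSK2141795 Safety Profile (Section 2.2.2) reports that "both intravenous and sliding scale insulin have been helpful". The Hypoglycemia paragraph beside it mentions no treatment. This shows what the authors meant, but it is background and does not amend the table. No other section restricts the bullet.

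**Step 3: is the literal reading consistent with the rest of the row?** Bullet 2 says "However the action of antihyperglycemic agents would be restored as GSK2141795 is cleared", and then "The patient should be observed closely for rebound hypoglycaemia as GSK2141795 is held/or discontinued". The row orders a hold for both triggers. A patient below 70 mg/dL would therefore be given insulin just as insulin sensitivity was returning. The literal reading conflicts with the row's own warning, so the fault is a missing qualifier and not a deliberate instruction.

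**Step 4: how foreseeable is the low-glucose trigger?** The documents point both ways.

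- *Toward foreseeable.* Section 2.2.2 lists hypoglycemia among commonly observed events in 151 subjects on GSK2141795 alone or with trametinib. The risk list in Section 7.1.1.2 places it in the column for events at 20% or less. Section 6.2 names it as a typical GSK2141795 toxicity and notes that single-agent toxicities may be stronger in combination. Section 2.2.2 calls the events asymptomatic, so the row could be entered on a meter reading alone.
- *Toward infrequent.* Section 2.2.2 describes hypoglycemia at 75 mg/day and above, with grade 3 or 4 events at 75 mg and 100 mg. Part 2 uses 50 mg, reducible to 25 mg (Sections 5.2.2 and 6.2): 50/75 = 0.67 and 25/75 = 0.33 of the lowest dose with reported events.
- *Uninformative.* The adverse events named for the 23-patient combination study (Section 2.2.3) do not include hypoglycemia, but that list gives only the most common events, at 10% or more.

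No rate at 50 mg or 25 mg is given, so an expected number of patients cannot be derived.

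**The case against.** The strongest reply is that no physician would misread the line. It follows directly on a bullet about hyperglycemia and insulin action, so context supplies the condition. Intravenous insulin is given by clinicians, so a patient could not act on the line alone. Low readings already go to the study doctor, drug is held, the investigator is told at once and intervention is discussed with the CTEP monitor. Section 6.2 describes its dose modifications as general guidelines. The PDF may also have nested the insulin bullet under the hyperglycemia one and lost that in extraction. Finally, Section 13.2 reports in the past tense that 50 patients were consented to obtain 37 evaluable, so few may still benefit.

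Most of this stands as an argument about likelihood, and it is why the point is minor. It does not make the sentence correct: every safeguard listed works by having someone recognize that the written recommendation should not be followed. Nesting is possible, but the text shows three bullets at one level. A further criticism is fair: qualifying the insulin bullet still leaves the row with no treatment guidance for glucose below 70 mg/dL beyond holding drug and notifying the investigator.

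**Conclusion.** The concern holds. As written, the Moderate to Severe row recommends intravenous insulin for its low-glucose trigger as well as its high-glucose one. It is a drafting slip with clear intent: one bullet of three, in one row, for one of two triggers. It should be corrected because it is live safety text, but harm is unlikely. No endpoint, sample size, stopping rule or analysis is affected.

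The conclusion rests on the bullets standing at the same level in the source table. If the insulin bullet is in fact nested under the hyperglycemia one, the ambiguity is smaller. The benefit is limited to patients still in Part 2 or yet to enter it.

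**What to change.** Open the third bullet with the missing condition, *For blood glucose above 250 mg/dL*, and leave the rest of that sentence as it is. This matches the form of the first bullet. Leave the other two bullets unchanged, and keep the hold-and-notify instruction for both triggers.

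The clinical team may also wish to add a line on managing glucose below 70 mg/dL. That would be useful but goes beyond this correction.

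The cost is a few words in one table cell. Intended management, data collection and analysis do not change.
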